## **Action Taken with Study Drug**

Action taken with study drug in relation to each adverse event will be characterized as follows:

- None
- Drug withdrawn
- Drug interrupted
- Dose reduction
- Unknown
- Not applicable
- Other (specify on eCRF)

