## 10.4 Safety Analyses

Safety assessments of interest are local tolerability assessments, AEs, laboratory evaluations, and vital signs.

Safety analysis will be performed by treatment received for the Safety Population. Treatment-emergent adverse event descriptions will be mapped to standard terms, i.e., Medical Dictionary for Regulatory Activities (MedDRA) system organ class and preferred term. At each post-baseline visit, the number and proportion of subjects reporting any given TEAE will be tabulated cumulatively by severity; each subject will be counted only once according to the worst severity reported up to the current visit. Separate tables will be constructed for (a) all reported TEAEs, (b) protocol treatment-related TEAEs, (c) serious TEAEs, (d) TEAEs leading to protocol treatment discontinuation, (e) protocol treatment-related serious TEAEs, (f) severe TEAEs, (g) TEAEs leading to dose interruption, (h) TEAEs of special interest, and (i) anticholinergic TEAEs.

At each visit, local tolerability assessments will be descriptively summarized by severity. For any symptoms, subject severity is the worst severity of the two axillae.

An overall summary table will also be presented with subject incidences tabulated according to the worst severity experienced while on study. In addition, at each post-baseline visit, local tolerability will be summarized as cumulative shift tables versus baseline. Subject counts for each symptom will be cross-tabulated with baseline severity according to the maximum post-baseline severity reported for either axilla up to the current visit.

Laboratory parameters will be descriptively summarized (mean, standard deviation, median, minimum, maximum) for values obtained at Visit 1 and Visit 12. Whereas, vital signs will be summarized in a similar manner at each visit.

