## 5. STUDY SUBJECTS

## 5.1 Disposition of Subjects

Subject disposition will be summarized by treatment group for Safety, ITT, mITT, and PP populations separately. Summaries will include the number and percentage of subjects completing treatment, completing the study, and discontinuing the study early by the primary reason for discontinuation. The number and percentage of subjects excluded and reason for exclusion will be included in the PP population disposition table.

All subject disposition data will be listed by clinical site.

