#### 9.2 Adverse Events

Treatment-emergent adverse events (TEAEs) are defined as those adverse events (AEs) with onset during or after the first dose of study drug or existing events that worsened after the first dose during the study. Treatment-emergent AEs will be summarized by treatment group and severity.

Partial or completely missing AE start dates will be imputed as follows:

- 1. If the year and month are known:
  - a. If the year and month are the same as the year and month of the treatment start date, impute to treatment start date.
  - b. Otherwise, use the 1st of the month.
- 2. If only the year is known:
  - a. If the year is the same as the year of treatment start date, impute to treatment start date.
  - b. Otherwise, impute to January 1st of that year.
- 3. If the date is completely missing, impute to treatment start date.

Partial or completely missing AE end dates will be imputed in the same manner, with end of treatment date or end of study date.

AE listings will display the imputed dates.

Verbatim terms on case report forms will be mapped to preferred terms and system organ classes using the latest version of MedDRA.

Version: 2.0 Page 39 of 74

At Visits 5, 6, 7, 8, 9, 12 (EOT), and 13 (Follow-up), treatment-emergent adverse events (TEAEs) in the Safety Population will be summarized by severity in the following tables: all reported TEAEs, all SAEs, all treatment-related SAEs, treatment-related TEAEs, severe TEAEs, TEAEs leading to dose interruption, TEAEs leading to study discontinuation, TEAEs of special interest, and anticholinergic TEAEs. Additionally, local site reaction TEAEs will be summarized in the Safety Population by severity at Visits 5, 6, 7, 8, 9, 12 (EOT), and Visit 13 (Follow-up). Local site reaction TEAEs are defined as AEs coded to the system organ class of general disorders and administration site conditions and, at a minimum, the following preferred terms:

- Application site pruritus
- Application site pain
- Application site irritation
- Application site dermatitis
- Application site rash
- Application site erythema
- Application site discolouration
- Application site dryness
- Application site exfoliation
- Application site reaction
- Application site warmth

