Each of the above tables will be produced for cumulative TEAEs up to the current visit reported by all Safety Population subjects (including those absent from the current visit). At each of the visits, each of the above tables will summarize the subject incidence (frequency count and %) for the specified TEAE, mapped to MedDRA System Organ Class and Preferred Term, according to the highest severity reported. Subjects with only unknown severity for a TEAE will be counted under the severity unknown category.

Summaries that are displayed by system organ class and preferred terms will be ordered by descending incidence of system organ class in the total column and preferred term within each system organ class. The total column will not be displayed and will only be used for sorting. TEAEs of special interest include the following:

- Vision blurred
- Mydriasis (unilateral or bilateral)
- Urinary hesitation

An overall TEAE summary table by treatment group with the total number of TEAEs and the number and percentage of subjects with at least one of the following will be presented: TEAE, serious TEAE, treatment-related TEAE, treatment-related serious TEAE, severe TEAE, TEAE leading to dose interruption, TEAE leading to study discontinuation, TEAEs of special interest, anticholinergic TEAEs, anticholinergic TEAEs leading to study discontinuation, local site reaction TEAEs, local site reaction TEAEs leading to study discontinuation. The overall summary table will also display the number and percent of subject deaths, should any deaths occur.

Version: 2.0 Page 40 of 74

The number of subjects with study discontinuations due to TEAEs, the number of subjects with study discontinuations due to anticholinergic TEAEs, and the number of subjects with study discontinuations due to AESIs will be plotted as a bar chart versus time on treatment. Time on treatment is defined as the earlier of treatment end date or study discontinuation date – treatment start date + 1. Time on treatment will be displayed in categories of 0 to 2 weeks, >2 to 4 weeks, >4 to 6 weeks. Weeks are defined as 7 days. The follow-up visit is excluded.

The number of treatment-related TEAEs and the number of local site reaction TEAEs will be plotted versus time on treatment. The number of subjects with a treatment-related TEAE and the number of subjects with a local site reaction TEAE will be plotted versus time. Time for these plots will be displayed as weeks 1-8 which includes the follow-up visit.

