Adverse event data will be presented in data listings by subject, treatment group, and event. SAEs, TEAEs leading to study discontinuation, TEAEs of special interest, and anticholinergic TEAEs will be presented in separate data listings. Death is not expected. However, should death occur on study, the event will be reported with detailed narratives.

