## 13. CHANGES TO THE ANALYSES PLANNED IN THE PROTOCOL

Due to the issue of duplicate subjects discussed in Section 3.3, the mITT analysis population was added. Definition of local site reaction TEAEs and analysis of local site reaction TEAEs was added.

Version: 2.0 Page 47 of 74

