14.3.1.2.8	Number and Percentage of Subjects with Treatment- Emergent Adverse Events of Special Interest Cumulative to Visit 5 (Day 8) by System Organ Class, Preferred Term, and Maximum Severity	Safety
14.3.1.2.9	Number and Percentage of Subjects with Anticholinergic Treatment-Emergent Adverse Events Cumulative to Visit 5 (Day 8) by System Organ Class, Preferred Term, and Maximum Severity	Safety
14.3.1.2.10	Number and Percentage of Subjects with Local Site Reaction Treatment-Emergent Adverse Events Cumulative to Visit 5 (Day 8) by System Organ Class, Preferred Term, and Maximum Severity	Safety
14.3.1.3.1	Number and Percentage of Subjects with Treatment- Emergent Adverse Events Cumulative to Visit 6 (Day 15) by System Organ Class, Preferred Term, and Maximum Severity	Safety
14.3.1.3.2	Number and Percentage of Subjects with Serious Treatment-Emergent Adverse Events Cumulative to Visit 6 (Day 15) by System Organ Class, Preferred Term, and Maximum Severity	Safety
14.3.1.3.3	Number and Percentage of Subjects with Serious Treatment-Related Treatment-Emergent Adverse Events Cumulative to Visit 6 (Day 15) by System Organ Class, Preferred Term, and Maximum Severity	Safety
14.3.1.3.4	Number and Percentage of Subjects with Treatment-Related Treatment-Emergent Adverse Events Cumulative to Visit 6 (Day 15) by System Organ Class, Preferred Term, and Maximum Severity	Safety
14.3.1.3.5	Number and Percentage of Subjects with Severe Treatment-Emergent Adverse Events Cumulative to Visit 6 (Day 15) by System Organ Class, Preferred Term, and Maximum Severity	Safety
14.3.1.3.6	Number and Percentage of Subjects with Treatment- Emergent Adverse Events Leading to Dose Interruption Cumulative to Visit 6 (Day 15) by System Organ Class, Preferred Term, and Maximum Severity	Safety
14.3.1.3.7	Number and Percentage of Subjects with Treatment- Emergent Adverse Events Leading to Study Discontinuation Cumulative to Visit 6 (Day 15) by System Organ Class, Preferred Term, and Maximum Severity	Safety

Version: 2.0 Page 58 of 74

Number	Title	Population
14.3.1.3.8	Number and Percentage of Subjects with Treatment- Emergent Adverse Events of Special Interest Cumulative to Visit 6 (Day 15) by System Organ Class, Preferred Term, and Maximum Severity	Safety
14.3.1.3.9	Number and Percentage of Subjects with Anticholinergic Treatment-Emergent Adverse Events Cumulative to Visit 6 (Day 15) by System Organ Class, Preferred Term, and Maximum Severity	Safety

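### The SAP replaces the protocol's table of TEAEs leading to treatment discontinuation with study discontinuation and does not declare the change

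*SAP*

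**What the plan says.** Protocol Section 10.4 lists the TEAE tables to be produced and includes "d) TEAEs leading to protocol treatment discontinuation". The synopsis has the same list. TEAEs leading to dose interruption are a separate item (g).

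SAP Section 9.2 gives the corresponding by-visit tables as "TEAEs leading to dose interruption, TEAEs leading to study discontinuation, TEAEs of special interest". The overall TEAE summary repeats this: "TEAE leading to dose interruption, TEAE leading to study discontinuation, TEAEs of special interest". So does the sentence on separate listings: "SAEs, TEAEs leading to study discontinuation, TEAEs of special interest, and anticholinergic TEAEs will be presented in separate data listings". The shells in SAP Section 15 follow suit, for example "Emergent Adverse Events Leading to Study Discontinuation Cumulative to Visit 6 (Day 15) by" system organ class, preferred term and maximum severity.

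SAP Section 13, which records departures from the protocol's analyses, states that "the mITT analysis population was added" and that the definition and analysis of local site reaction TEAEs were added. It says nothing about discontinuation.

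**The concern.** A safety table named in the protocol has no counterpart in the SAP, and a similar-sounding one stands in its place. SAP Section 1 says that the SAP is based on protocol Amendment 3 and that changes from the protocol's analyses will be documented in the SAP. This one is not.

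AEs that made subjects give up the drug are a standard tolerability result, and safety and local tolerability is the first objective listed in the protocol. If stopping the gel and leaving the study always coincided, the change of wording would be harmless. The documents do not make them coincide. Where they part, the study-discontinuation count can only be the smaller of the two for subjects who stopped the gel because of an AE.

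**Working it through.** The point turns on wording, so there is no formula to apply and no figure in the plan to reproduce. The check has three steps.

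**1. Which outputs use which event?**

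| Source | Treatment discontinuation | Study discontinuation |
|---|---|---|
| Protocol synopsis and 10.4(d) | Planned table | Not listed |
| SAP by-visit tables 14.3.1.2.7 to 14.3.1.8.7 | 0 | 7 tables |
| SAP overall summary 14.3.1.1, as described in 9.2 | 0 | 3 rows (all, anticholinergic, local site reaction) |
| SAP figures 14.3.1.1.1 to 14.3.1.1.3 | 0 | 3 figures |
| SAP listing 14.3.2.2 | 0 | 1 listing |

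The substitution is complete and consistent, so it is not a slip in one place.

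**2. Can the two events differ under the documents?**

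- The protocol's list of actions taken with study drug (Section 9.2.1.2) includes "Drug withdrawn" and has a separate code for interruption. The action is recorded on the eCRF for each AE.
- Protocol Section 7.4 says that a subject may be discontinued from the study after an AE or because of intolerance. The wording is permissive.
- Protocol Section 9.2.1, on laboratory abnormalities, names ending the study and stopping study treatment as separate outcomes.

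So a subject can have an AE with the drug withdrawn and still complete the study.

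**3. Where would that subject appear?**

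- Study-discontinuation tables, summary rows, figures and listing: no, because the subject did not leave the study.
- Dose-interruption table: uncertain. Withdrawal and interruption are different codes, and the SAP text does not define the filter for this table.
- Disposition: SAP Section 5.1 reports subjects "completing treatment, completing the study, and discontinuing the study early", with a primary reason for early study discontinuation. The subject would lower the treatment-completion count, but the summary as described gives no AE reason for that.
- All-TEAE tables and AE listing 16.2.7.1: yes. The treatment-related, severe, anticholinergic, special-interest and local-site tables would also show the event where it qualifies.
- Exposure summary and dosing listing 16.2.5.1: the early stop would show, without being tied to the AE.

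What is lost is the classification of the event as one that ended treatment.

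**The case against.** The strongest reply is that the documents plan no route for a subject who stops the gel and stays. Section 7.4 is the protocol's only section on early discontinuation. It treats a significant-risk AE and intolerance of the product as grounds for leaving the study, and it sets no off-drug visit schedule. SAP Section 8.2.1.1, in describing the imputation, moves from stopping treatment to dropping out as if they were one event. Protocol Sections 8.1.4 and 8.1.5 also sort the consequences of an AE into interruption of treatment or discontinuation from the study, with no third class. On this view the SAP follows a usage already in the protocol, and the two tables might be nearly identical. That stands as a limit on size. It does not remove the gap, because Section 7.4 is permissive, the eCRF codes withdrawal separately, and Section 10.4(d) asks for the treatment table by name.

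Three stronger readings are tempting, and the documents do not support them.

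- **That the separate counts of completing treatment and completing the study show that off-drug subjects are expected.** They do not. Treatment lasts 42 days and follow-up is at Day 57, so a subject can finish the gel and miss the last visit. The separate treatment-end and study-discontinuation dates in SAP Section 9.2 have the same explanation. The estimands' indifference to adherence defines whom the analysis covers; it is not a retention procedure.
- **That the undercount can be quantified by assuming a withdrawal rate and a share who still attend Visit 12.** Neither rate is in the documents. Attending Visit 12 also does not mean staying in the study, since Section 7.4 asks early discontinuers to complete those evaluations, and they would be counted.
- **That the AEs vanish from the report.** They remain in the all-TEAE tables and the full listing.

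**Conclusion.** The discrepancy is real and undeclared. The protocol specifies TEAEs leading to treatment discontinuation; the SAP provides none and uses study discontinuation throughout. A subject who permanently stops the gel for an AE but completes the study would be absent from every study-discontinuation summary, and might be absent from the interruption table too.

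The size is unknown and may be small. The conclusion rests on reading Section 7.4 as permissive and on the action-taken codes meaning what they say. It also rests on the SAP text alone: the table specifications are in a separate document, which might define the filters differently. The tables are descriptive, with no hypothesis test, and neither co-primary result is affected. This is a minor safety-reporting correction.

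**What to change.** Add TEAEs leading to treatment discontinuation, defined as TEAEs with action taken "Drug withdrawn", to the overall TEAE summary, the by-visit tables and a listing, as protocol Section 10.4(d) specifies. Keep the study-discontinuation outputs as additional rows and declare them in SAP Section 13 as additions to the protocol plan. State in Section 9.2 which eCRF field selects events for each of the three classes: interruption, treatment discontinuation and study discontinuation.

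The cost is a few lines of SAP text and one filter on a field already collected for each AE. No new data are needed and nothing changes in the conduct of the trial. If the database is already locked, SAP Section 1 allows supplementary analyses that are described in the clinical study report, so the output can still be produced there.

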## 1 BACKGROUND AND CLINICAL RATIONALE

Hyperhidrosis is a disorder of excessive sweating beyond what is expected for thermoregulatory needs and environmental conditions. Primary hyperhidrosis (excessive sweating without an alternative origin) is localized, characteristically symmetric, and may involve several anatomic areas such as armpits, hands, and feet. It affects approximately 4.8% of the United States (US) population (Doolittle, 2016) and is believed to be caused by an overactive cholinergic response of the sweat glands. Current therapies have limited efficacy, significant side effects, and/or are invasive and costly.

Oral and topical anticholinergic drugs, such as glycopyrrolate, have been used to treat hyperhidrosis. The main limitations of these drugs are systemic anticholinergic side effects (e.g., blurred vision, dizziness, dry mouth, constipation, urinary retention, and tachycardia). Sofpironium bromide is a novel, soft-anticholinergic ester analog of glycopyrrolate and is in development for the topical treatment of axillary hyperhidrosis.

Sofpironium bromide is a competitive inhibitor of acetylcholine receptors located on certain peripheral tissues, including sweat glands. Sofpironium bromide gel is expected to inhibit the action of acetylcholine in sweat glands, thereby reducing the extent of sweating, and as a soft drug, is designed to provide maximal therapeutic effect with minimal side effects. Please refer to the sofpironium bromide gel Investigator's Brochure for more information.

In the current multicenter, randomized, double-blinded, vehicle-controlled, pivotal, Phase 3 study, Brickell is studying the safety, tolerability, and efficacy of topically applied sofpironium bromide gel, 15%, in subjects with primary axillary hyperhidrosis over a 6-week period, followed by a 2-week follow-up period.

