#### Risk to Subjects

As an anticholinergic drug, administration of sofpironium bromide gel could be associated with signs or symptoms typical of anticholinergic effect such as dry mouth, blurred vision, dizziness, constipation, urinary retention, or tachycardia. The previous sofpironium bromide exposure to humans has demonstrated a low incidence of these effects, which are generally mild in severity. All such effects have been observed, and as expected, to be transient.

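### The SAP's special-interest adverse event list has urinary hesitation but not urinary retention, the urinary risk named in the protocol

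*SAP*

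**What the plan says.** SAP 9.2 introduces its list with "TEAEs of special interest include the following" and gives three terms: blurred vision, mydriasis of one or both eyes, and "Urinary hesitation". No other part of the SAP adds a term, and urinary retention is not mentioned anywhere in it.

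Protocol 10.4, like the synopsis, calls for separate tables that include "h) TEAEs of special interest, and (i) anticholinergic TEAEs", but defines neither group.

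Protocol section 1, under Risk to Subjects, says the study drug could be associated with signs or symptoms typical of "anticholinergic effect such as dry mouth, blurred vision, dizziness, constipation, urinary retention, or tachycardia". The opening of section 1 gives the same six effects for oral and topical anticholinergic drugs as a class: "blurred vision, dizziness, dry mouth, constipation, urinary retention, and tachycardia". Urinary hesitation is not mentioned anywhere in the protocol.

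For comparison, SAP 9.2 defines local site reactions by a system organ class "and, at a minimum, the following preferred terms", followed by eleven named terms.

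**The concern.** By putting a urinary term on the list, the sponsor marked a urinary effect for targeted reporting. The term chosen is not the one the protocol names as a risk of the study drug. A reader who turns to the special-interest outputs for urinary effects could find none, although an event of the kind named in the protocol had been reported. The special-interest discontinuation figure could likewise omit a subject who left the study because of such an event. The stake is the completeness of one set of descriptive safety outputs.

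**Working it through.** No arithmetic beyond counting applies. The check compares the term lists and then follows an event coded to retention through the planned outputs.

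**Step 1. Terms side by side.**

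| Effect | Protocol, Risk to Subjects (study drug) | Protocol, opening of section 1 (drug class) | SAP 9.2 special-interest list |
|---|---|---|---|
| Blurred vision | yes | yes | yes |
| Urinary retention | yes | yes | no |
| Dry mouth | yes | yes | no |
| Dizziness | yes | yes | no |
| Constipation | yes | yes | no |
| Tachycardia | yes | yes | no |
| Mydriasis | no | no | yes |
| Urinary hesitation | no | no | yes |

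One of the six named risks is on the list. Two of the three listed terms are not among the named risks. The two documents both address a urinary effect, but with different terms.

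**Step 2. Is there another definition?** The protocol asks for the table without listing terms. SAP section 13, on changes from the protocol, does not discuss the list. The list in SAP 9.2 is therefore the only definition available.

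**Step 3. What happens to an event coded to retention?** SAP 9.2 maps reported terms to MedDRA preferred terms and tabulates by them. An event coded only to urinary retention matches none of the three listed terms. On the plain reading it is missing from:

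- seven by-visit tables, 14.3.1.2.8 to 14.3.1.8.8 (Visits 5, 6, 7, 8, 9, 12 and 13);
- the special-interest row of Table 14.3.1.1;
- Figure 14.3.1.1.3;
- Listing 16.2.7.2.

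That is 7 + 1 + 1 + 1 = 10 places.

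**Step 4. Where would it still be seen?**

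- Always: the by-visit tables of all TEAEs and Listing 16.2.7.1.
- If it qualified: the treatment-related, serious, severe, dose-interruption and discontinuation tables, and Figure 14.3.1.1.1 if the subject discontinued because of it.
- Probably: the anticholinergic outputs, namely Tables 14.3.1.2.9 to 14.3.1.8.9, the anticholinergic rows of Table 14.3.1.1, Figure 14.3.1.1.2 and Listing 16.2.7.3. The protocol itself describes retention as a typical anticholinergic effect. Neither document lists the terms for this group, so this route is likely but not confirmed.

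**The case against.** The strongest reply is that the documents do not contradict each other. No section says that the special-interest list must follow the protocol's risk statement. Four other named risks are also off the list, and mydriasis is on it without being named, so the list evidently came from another source. That source may be the Investigator's Brochure, to which the protocol refers and which is not available here. Choosing these terms is a sponsor's safety judgement. This stands, and it is why the fix leaves room for a stated reason.

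A second reply is that the SAP says its events of special interest include three terms, which may leave the list open, and that SAP section 1 places the table, figure and listing specifications in a separate document. This stands in part. The same section of the SAP marks a list as a minimum when it means one, and does not do so here. If the list is open, no rule says what else belongs in it, so a clarifying statement is needed on either reading.

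A third reply is that nothing is lost, since the event appears in the all-TEAE outputs and probably in the anticholinergic ones. This stands, and it limits the point to the special-interest outputs.

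A reader might also infer that the plan drops the more serious urinary event and that each missed case would be clinically significant. The documents do not support this: neither ranks retention above hesitation, and the point does not need such a ranking.

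**Conclusion.** The mismatch holds, and it is minor. On the plain reading of SAP 9.2, an event coded only to urinary retention is absent from the ten special-interest places counted above, so those outputs could show no urinary event when one had occurred.

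This rests on two assumptions: that the three-term list is closed, and that the separate output specifications add nothing to it.

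The number of events should be small. The protocol reports a low incidence of anticholinergic effects with the study drug. Its exclusion criterion 9 covers obstructive uropathy and benign prostatic hyperplasia where the investigator judges that they may alter sweating or be made worse by anticholinergics. Safety analyses are descriptive, without hypothesis testing, and efficacy conclusions are unaffected.

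It would go too far to infer that retention is hidden from safety reporting, or that every risk named in the protocol must be of special interest. The absence of a written term list for anticholinergic events is missing detail; it does not show that retention would be left out of that group.

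**What to change.** Before unblinding, add the preferred term Urinary retention to the special-interest list in SAP 9.2 and state that the list is exhaustive. If hesitation alone was intended, keep the list, say so, and reconcile the choice with the protocol's risk statement by giving the reason.

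The cost is one line in the SAP and one more term in the programming flag, with no new data. The special-interest count can only stay the same or rise, so the change cannot hide a signal.
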